7. ADVERSE EVENTS AND REPORTING PROCEDURES

7.1 Potential Adverse Events

Potential risks associated with dilute HOCl are skin itching and skin irritation. Prior human clinical trials demonstrated no significant risk of dilute 0.005% hypochlorite. One patient had itching and mild skin irritation. Because we are diluting the hypochlorite, we do not have significant concern for using concentrations that are too high.

7.2 Adverse Event Reporting

Adverse events will be graded according to CTCAE v4.03 and Stanford Radiation Dermatitis Scoring System. Both Serious and Non-Serious Adverse Events will be clearly noted in source documentation and listed on study specific Case Report Forms (CRFs). The Protocol Director (PD) or designee will assess each Adverse Event (AE) to determine whether it is unexpected according to the Informed Consent, Protocol Document, or Investigator's Brochure, and related to the investigation. All Serious Adverse Events (SAEs) will be tracked until resolution, or until 30 after the last dose of the study treatment.

Skin-related SAEs CTCAE Grade 4 and above, and all subsequent follow-up reports will be reported to the Stanford Cancer Institute Data and Safety Monitoring Committee (DSMC) using the study specific CRF regardless of the event's relatedness to the investigation. Following review by the DSMC, events meeting the IRB definition of 'Unanticipated Problem' will be reported to the IRB using eProtocol within 10 working days of DSMC review, or within 5 working days for deaths or life-threatening experiences.

8. CORRELATIVE STUDIES

There will be no correlative studies involved in this investigation.

9. STUDY CALENDAR

	Baseline prior to	During Radiation Treatment	Follow-Up
	Radiation		(3-12 weeks)
	Treatment		
Randomization	Х		
Blinded Solution		X ^A	
Application			
(HOCl vs			
placebo)			
HOCl Treatment		X ^B	
Clinical Skin	Х	X ^C	Х
Assessment			
QOL/Pain	Х	X ^{D, E}	Х
Questionnaire			
Photos of Neck	Х	X ^{D, E}	Х

A: Applied each day for 10 minutes within 3 hours of radiation treatment

B: Starting at the onset of Grade E Radiation Dermatitis during radiation treatment, HOCl will be applied as treatment per standard of care for both study arms

C: Performed once weekly by the treating physician and on the last day of radiation treatment +/- 10 days

D: Administered at 40-50 Gy of radiation treatment

E: Administered on the last day of radiation treatment +/- 10 days

10. MEASUREMENTS

10.1 Assessment of Outcome

Patients will be assessed on a weekly basis during radiation treatment as per standard of care. At each weekly on-treatment visit, a clinical skin assessment (physical exam) will be performed and documented per standard of care.

In addition to standard management, all patients enrolled on this study will be required to have photos of the neck taken at four time points: at the time of randomization, at 40-50 Gy of radiation treatment, at the end of radiation treatment \pm 10 days, and at the follow-up visit 3-12 weeks after completion of radiation treatment. To ensure consistency, photos will be taken with standardized equipment.

10.2 Inter-Rater Reliability

Patients enrolled on this study will be treated by experienced radiation oncologists. Inter-rater reliability will be established by a run-in training session. Prior to opening the study for accrual, these physicians will undergo a training session for the grading of radiation dermatitis. The training session will involve the physicians' review of 10 photos of the neck of patients undergoing treatment for head and neck cancer at various time points during treatment. Physicians will be blinded to the time point of the photo but will have access to the documented skin exam at the time the photo was taken. Each physician will assign a grade of radiation dermatitis for each photo, and the results will be assessed for reliability between the physicians with kappa statistics. A target kappa statistic of 0.8 will define good inter-rater reliability. If the target kappa statistic after the first set of photos is not met, the physicians will discuss and come to a consensus for each photo. A second set of 10 photos will then be assessed individually, and the kappa statistic will be again calculated. This process will be repeated for three iterations or until the target kappa score of 0.8 is met, whichever comes first.

If the kappa statistic of 0.8 is not met, a jurisdiction will be held every three months during the accrual of the trial. The jurisdiction will involve both physicians reviewing every photo of every patient enrolled since the previous jurisdiction (or start of the trial in case of the first jurisdiction). For the photos on which there is disagreement, the physicians will meet to discuss and come to a consensus grade for each photo. The consensus grade will be recorded as the final grade for that photo.

If the target kappa statistic of 0.8 is met and good inter-rater reliability is established, then spot-checks will be performed every three months during the accrual of the trial. A spot-check will involve the physicians assessing a set of the same 5 randomly-selected photos.

10.3 Primary Outcome

The primary outcome is the proportion of patients who experience Grade E radiation dermatitis as defined by the Stanford Radiation Dermatitis Scoring System in each arm of the study.

10.3.1 Measurement Methods

The primary outcome will be assessed and graded by the treating physician, a radiation oncologist, who will give an individual score of the irradiated area at baseline, once weekly during radiation treatment course, at the end of the radiation treatment course +/- 10 days, and at the patient's follow up visit 3-12 weeks after completion of the radiation treatment course. The final grading of radiation dermatitis for each time point will be subject to the inter-rater reliability processes described in Section 10.2.

10.4 Secondary Outcomes

The secondary outcomes are to assess the time to development of Grade E radiation dermatitis and the quality of life and level of pain before, during, and after radiotherapy.

10.4.1 Measurement Methods

Patients will be seen once weekly during radiation therapy by the treating physician, who will perform the weekly clinical skin assessments. At the time Grade E radiation dermatitis develops, the study coordinator will be notified, and the patient will be switched to standard management for radiation dermatitis.

The MBPI will be administered at the time of randomization, at 40-50 Gy of radiation treatment, at the end of radiation treatment +/- 10 days, and at the follow-up visit 3-12 weeks after completion of radiation treatment.

11. REGULATORY CONSIDERATIONS

11.1 Institutional Review of Protocol

The protocol, the proposed informed consent and all forms of participant information related to the study (e.g. advertisements used to recruit participants) will be reviewed and approved by the Stanford IRB and Stanford Cancer Institute Scientific Review Committee (SRC). Any changes made to the protocol will be submitted as a modification and will be approved by the IRB prior to implementation. The Protocol Director will disseminate the protocol amendment information to all participating investigators.

11.2 Data and Safety Monitoring Plan

The Stanford Cancer Institute Data and Safety Monitoring Committee (DSMC) will be the monitoring entity for this study. The DSMC will audit study-related activities to determine whether the study has been conducted in accordance with the protocol, local standard operating procedures, FDA regulations, and Good Clinical Practice (GCP). This may include review of the following types of documents participating in the study: regulatory binders, case report forms, eligibility checklists, and source documents. In addition, the DSMC will regularly review serious adverse events and protocol deviations associated with the research to ensure the protection of human subjects. Results of the DSMC audit will be communicated to the IRB and the appropriate regulatory authorities at the time of continuing review, or in an expedited fashion, as needed.

12. STATISTICAL CONSIDERATIONS

12.1 Randomization Method

Block randomization will be used to stratify by type of chemotherapy: cisplatin, cetuximab, no chemotherapy.

12.2 Sample Size Justification

The primary endpoint is the proportion of patients who develop Grade E radiation dermatitis (as defined by the Stanford Radiation Dermatitis Scoring System) in each arm during a course of radiation therapy. From prior clinical experience, we anticipate that 80% of patients will experience Grade E radiation dermatitis with standard skin care. In order to detect a 20% reduction in patients with Grade E radiation dermatitis (80% vs 60% in those treated with dilute hypochlorite solution) with Type I error of 0.05 and Type II error of 20% (power of 80%), 170 patients will be enrolled.

12.3 Primary Analysis

The primary endpoint is the proportion of patients who develop Grade E radiation dermatitis (as defined by the Stanford Radiation Dermatitis Scoring System) in each arm during a course of radiation therapy. A multiple logistic regression model will be used controlling for type of chemotherapy (cisplatin, cetuximab, none).

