APPENDIX A: PARTICIPANT ELIGIBILITY CHECKLIST	
APPENDIX B: STANFORD RADIATION DERMATITIS SCORING SYSTEM	
APPENDIX C: CTCAE Verson 4.03 For Radiation Dermatitis	
APPENDIX D: MODIFIED BRIEF PAIN INVENTORY	

PROTOCOL SYNOPSIS

TITLE	Randomized Study of Topical Dilute Hypochlorite for the		
	Prevention of Radiation Dermatitis in Head and Neck Cancer		
STUDY PHASE	Phase III		
STUDY REAGENT	1:1000 dilute hypochlorite solution (0.005%) administered to the skin prior to daily radiation therapy		
PRIMARY OBJECTIVE(S)	The primary objective is to determine whether prophylactic topical dilute HOCl reduces the proportion of patients who develop Grade E radiation dermatitis as scored on the Stanford Radiation Dermatitis Scoring System (SRDSS)		
SECONDARY OBJECTIVE(S)	 Secondary objectives are: To determine whether this agent delays the time to development of Grade E radiation dermatitis To determine whether this agent improves quality-of-life and pain scores associated with radiation dermatitis 		
TREATMENT SUMMARY	Eligible patients will be randomized to daily application of topical dilute hypochlorite versus placebo for 10 minutes within 3 hours prior to daily radiation treatment. When patients in either arm develop Grade E radiation dermatitis during the radiotherapy course, they will be switched to topical dilute hypochlorite treatment daily per standard of care. Patients will complete the Modified Brief Pain Inventory at study entry, at 40-50 Gy through the radiation treatment course, at the end of radiation treatment, and at the follow-up visit 3-12 weeks after radiation treatment.		
SAMPLE SIZE	170 Patients (85 patients per arm)		
STATISTICAL CONSIDERATIONS	Sample Size Calculation: From prior clinical experience, we anticipate that 80% of patients will experience Grade E radiation dermatitis with standard skin care. In order to detect a 20% reduction in patients with Grade E dermatitis (80% vs 60% in those treated with dilute hypochlorite solution) with a two-sided alpha of 0.05 and beta of 80%, 170 patients will be enrolled. Primary endpoint: The proportion of patients in each arm who develop Grade E radiation dermatitis (as defined by the Stanford Radiation Dermatitis Scoring System) during a course of		

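### Each patient's own physician grades the primary endpoint, but physician is not in the primary model, so an inexpensive gain in precision is left unused

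*Combined protocol and SAP*

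**What the plan says.** Section 12.3 gives the primary analysis in one sentence: "A multiple logistic regression model will be used controlling for type of chemotherapy (cisplatin, cetuximab, none". Section 12.1 stratifies randomization by the same factor and no other. Section 10.3.1 names the grader: "The primary outcome will be assessed and graded by the treating physician, a radiation oncologist". It also makes the final grade at each time point subject to the agreement process in Section 10.2.

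That process starts with training on sets of 10 photos, for up to three rounds, with a kappa target of 0.8.
- **Target missed:** the trial goes ahead with a review every three months, "both physicians reviewing every photo of every patient enrolled" since the last review. Disagreements are settled by consensus, and the consensus becomes the final grade for that photo.
- **Target met:** the later check is five photos every three months. No action is given if that check goes badly.

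Sections 4.1, 9 and 10.1 schedule photos at four time points, against weekly grading. Section 2.3 instead has photos taken at each clinical assessment. Section 2.3 also keeps the allocation from the treating physician.

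**The concern.** Grade E is a clinical judgement made by one person per patient, and that person differs between patients. Physicians may call moist desquamation at different rates or see different kinds of patient. Part of the variation in outcome then belongs to the physician and not to treatment. Section 2.3 adds room for this, because it ties Grade E to the need for treatment, whereas Appendix B defines it by moist desquamation alone.

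The treating physician can be identified at baseline: that physician does the baseline skin assessment (Section 4.1), and a physician signs the eligibility checklist (Appendix A). A model that omits the physician leaves a known baseline factor unused. At stake is precision in the primary comparison, and the estimate's exposure to chance imbalance in which physician graded which arm.

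**Working it through.** **1. The plan's own figure.** Inputs from Section 12.2: "we anticipate that 80% of patients will experience Grade E radiation dermatitis with standard skin care"; the contrast "80% vs 60% in those treated with dilute hypochlorite solution"; and "Type I error of 0.05 and Type II error of 20% (power of 80%), 170 patients will be enrolled". The Protocol Synopsis supplies the two-sided test and "170 Patients (85 patients per arm"). (Where it gives beta as 80%, power of 80% is meant, as in Section 12.2.)

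Pooled-variance formula: n per arm = [1.960·√(2·0.7·0.3) + 0.842·√(0.8·0.2 + 0.6·0.4)]² / 0.2² = (1.270 + 0.532)² / 0.04 = 81.2, so 82 per arm and 164 in total.

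Power at 85 per arm = Φ[(0.2·√85 − 1.270)/0.632] = Φ(0.907) = 81.8%. The planned 170 is a slight round-up of 164 and meets the 80% target.

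**2. Adding a physician term.** The assumptions below are not in the documents:
- two physicians with equal caseloads;
- a 50/20/30 chemotherapy mix with no effect on outcome;
- a stated gap between physicians in control-arm Grade E rate;
- a common odds ratio for treatment, with arm averages held at 80% and 60%.

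The main simulation used 5,000 trials of 170 patients per scenario, fitting arm + chemotherapy with and without physician. A separate simulation used 4,000 fits per scenario. Each cell shows power without → with the term.

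| Control-arm gap (rates by physician) | 5,000 trials | 4,000 fits |
|---|---|---|
| 0 (80/80) | 82.0% → 82.0% | 82.0% → 81.8% |
| 10 points (85/75) | 82.0% → 82.8% | 82.3% → 83.0% |
| 20 points (90/70) | 83.2% → 85.6% | 82.6% → 85.6% |
| 30 points (95/65) | 82.0% → 89.5% | 82.3% → 89.1% |

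The Monte Carlo standard error of one power figure is √(0.82·0.18/5000) = 0.5 points.

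The gaps are control-arm gaps, and a common odds ratio widens them in the experimental arm. At 20 points the log odds ratio is −1.070, a factor of 0.343. Odds of 9 become 3.09 (75.5%) and odds of 2.33 become 0.80 (44.5%), a gap of 31 points. The same step gives about 15 points for the 10-point row and 50 for the 30-point row. The lower rows are therefore strong assumptions.

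**3. Type I error, without vs with the term.** Gap 0: 5.1% vs 5.2%. Gap 20: 5.0% vs 5.0%. Gap 30: 4.5% vs 5.0%.

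**4. Chance imbalance.** The SD of the between-arm difference in one physician's share is √(2·0.25/85) = 7.7 points. If the same gap g holds in both arms, a 1-SD imbalance moves the risk difference by 0.077·g, which is 0.8, 1.5 or 2.3 points for gaps of 10, 20 or 30. At 1.96 SD it is 1.5, 3.0 or 4.5 points, against a target effect of 20.

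**The case against.** The strongest reply is that the existing model is sound. It is prespecified, it adjusts for the one stratification factor, and the grader is blinded to arm. The 80% and 60% rates already average over graders, so leaving physician out takes nothing from the planned power. Chance imbalance is ordinary sampling variation that the standard error already covers. All of that stands.

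A further reply is that Section 10.2 keeps any gap small. Take two graders, a yes/no Grade E call at 70% prevalence, and every disagreement in the same direction. Kappa 0.8 then allows a gap g = 0.2·(0.42 + g²/2), about 8.5 points; at 50% prevalence it allows about 10. These are per-assessment figures and only approximate for ever reaching Grade E, but they point to the 10-point row and a gain under 1 point. If the target is missed, consensus grading begins.

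This reply stands only in part:
- Observing kappa 0.8 on 10 photos does not establish it. Suppose true kappa is 0.6 at 50% prevalence, so the graders agree on 80% of photos. All 10 agree with probability 0.8¹⁰ = 0.107. Nine agree with probability 10·0.2·0.8⁹ = 0.268, and kappa then reaches 0.8 only if one grader has exactly five positives (49%), adding 0.132. The total is 24% per set, or 1 − 0.76³ = 56% within three sets, if no learning occurs between sets.
- Consensus covers photos only. On the four-time-point schedule, a Grade E first seen at another weekly visit may have no photo to review.
- Neither route removes case-mix differences between physicians.

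A reader might infer from Section 10.2 that the graders are known to differ, or that the trial simply accepts poor agreement. The documents support neither: no rater difference is reported, and a missed target triggers consensus review.

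**Conclusion.** The point holds as a forgone gain in precision. The physician grades the endpoint, is identifiable at baseline, and is in neither the stratification nor the primary model. The gain from including the term is about 1, 2 to 3 or 7 points of power for control-arm gaps of 10, 20 or 30 points, with no material cost at zero. The size rests on the assumed gaps and on two equal caseloads. Two graders are implied by Section 10.2 but not stated, and if the graders agree closely the gain is small.

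A reader might go further and infer a biased comparison, an invalid test or an underpowered trial. None follows. Allocation is randomized and concealed from the grader, type I error without the term is 4.5% to 5.1%, and power without it is 82% to 83%.

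**What to change.** - In Section 12.3, prespecify arm + chemotherapy type + treating (grading) physician as the primary logistic model. State the number of graders and a rule for pooling physicians with few patients.
- In Section 12.4, use the same terms in the Cox model for time to Grade E. The present rule, which adds characteristics if they prove significant, does not name physician and depends on the data.
- Do not extend the term to the pain and quality-of-life model on grading grounds, because those scores are patient-reported. Prescribed dose should not be added on this argument either: it was not examined here, and Appendix A shows only a yes/no item for a maximum below 45 Gy.
- Reconcile Section 2.3 with Sections 4.1, 9 and 10.1 on when photos are taken.

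The cost is a sentence or two of text and, with two graders, one degree of freedom. The treatment odds ratio also becomes conditional on physician and moves somewhat further from 1: in the 20-point scenario the mean log odds ratio is −1.02 without the term and −1.12 with it. The report should say which one is given. The choice must be fixed before outcome data are seen, since adding physician afterwards would be open to challenge.

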12.4 Secondary Analyses

Secondary endpoints include the time to development of Grade E radiation dermatitis and the qualityof-life and pain scores in each arm. Time to development of radiation dermatitis will be defined as time from Day 1 of radiation treatment to the first appearance of Grade E radiation dermatitis. This data will be summarized with Kaplan-Meier curves. A Cox proportional hazards model will be used to compare the treatment groups. The model will adjust for type of chemotherapy and other patient characteristics should they prove to be significant. A repeated measures model will be used to analyze the quality-oflife and pain scores. The model will adjust for type of chemotherapy and other patient characteristics should they prove to be significant.

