	radiation therapy will be assessed using a multiple logistic regression model adjusting for type of chemotherapy (cisplatin, cetuximab, none). Secondary endpoints: Time to development of Grade E radiation dermatitis in each arm will be assessed using the Cox proportional hazards model adjusting for type of chemotherapy. QOL/Pain scores will be analyzed using a repeated measures model adjusting for type of chemotherapy.		

SCHEMA

LIST OF ABBREVIATIONS AND DEFINITION OF TERMS

AE	Adverse event
CRF	Case report/Record form
CTCAE	Common Terminology Criteria for Adverse
	Events
DSMB	Data Safety Monitoring Board
HOCI	Hypochlorite
IRB	Institutional Review Board
MBPI	Modified Brief Pain Inventory
RR	Response Rate
SAE	Serious adverse event
SRDSS	Stanford Radiation Dermatitis Scoring System

1. **OBJECTIVES**

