1.2. Secondary Objectives

The secondary objectives include the time to development of Grade E radiation dermatitis and the quality-of-life and pain levels (as assessed by the Modified Brief Pain Inventory) in the control arm versus the experimental arm.

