2.3.1 Modified Brief Pain Inventory

Patients with moderate-severe radiation dermatitis often experience significant pain and discomfort until the skin heals, which can sometimes take up to 2-3 weeks. In order to assess patient reported levels of pain, patients will be asked to complete the Modified Brief Pain Inventory (MBPI) at the time of randomization, at 40-50 Gy of treatment, on the last day of radiation treatment +/- 10 days, and at the first follow-up visit 3-12 weeks after completion of the radiation treatment course. The MBPI allows patients to rate the severity of their pain as well as the degree to which their pain interferes with normal activities. There are seven pain severity items and seven pain interference items rated on a 0-10 Likert scale. It will take approximately 5 minutes to complete (ref; Appendix D).

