APPENDIX C: Modified Brief Pain Inventory

Please fill in the following: First Name (1) Last Name (2)

Time point for survey:

- **O** Baseline prior to radiation treatment (1)
- \bigcirc 40-50 Gy of radiation treatment (2)
- **O** Last day of radiation treatment (3)
- Follow-up visit 3-12 weeks after radiation treatment course (4)

Q1 Please rate your current level of skin discomfort.

- **O** 0 (0)
- **O** 1(1)
- **O** 2(2)
- **O** 3(3)
- $O_{4}(4)$
- **O** 5(5)
- **O** 6(6)
- **O** 7 (7)
- **O** 8 (8)
- O 9(9)
- **O** 10 (10)

Q2 Please rate your pain by selecting the one number that best describes your pain at its worst in the last 24 hours.

- **O** 0 (0)
- **O** 1(1)
- **O** 2 (2)
- **O** 3 (3)
- **O** 4 (4)
- **O** 5 (5)
- **O** 6 (6)
- **O** 7 (7)
- **O** 8 (8)
- O 9(9)
- **O** 10 (10)

Q3 Please rate your pain by selecting the one number that best describes your pain at its least in the last

24 hours.

- **O** 0 (0)
- **O** 1 (1)
- **O** 2 (2)
- **O** 3 (3) **O** 4 (4)
- O = 4 (4)O = 5 (5)
- O 6(6)
- **O** 7 (7)
- O = 8 (8)
- O 9(9)
- O 10(10)

Q4 Please rate your pain by selecting the one number that best describes your pain on the average.

- (0) 0 **C**
- **O** 1 (1)
- **O** 2 (2)
- **O** 3 (3)
- **O** 4 (4)
- **O** 5 (5)
- **O** 6(6)
- **O** 7(7)
- **O** 8 (8)
- **O** 9 (9)
- **O** 10 (10)

Q5 Please rate your pain by selecting the one number that tells how much pain you have right now.

- **O** 0 (0)
- **O** 1(1)
- **O** 2 (2)
- **O** 3 (3)
- **O** 4 (4)
- **O** 5 (5)
- **O** 6 (6)
- **O** 7 (7)
- **O** 8 (8) **O** 9 (9)
- O 10(10)

Q6 What treatments or medication are you receiving for your pain?

Q7 In the last 24 hours, how much relief have pain treatments or medications provided? Please select

the one percentage that most shows how much relief you have received?

- \bigcirc 0% (No Relief) (0)
- **O** 10% (1)
- **O** 20% (2)
- **O** 30% (3)
- **O** 40% (4)
- **O** 50% (5)
- **O** 60% (6)
- **O** 70% (7)
- **O** 80% (8)
- **O** 90% (9)
- \bigcirc 100% (Complete Relief) (10)

Select the one number that describes how, during the past 24 hours, pain has interfered with your:

Q8 General Activity

- **O** 0 (0)
- **O** 1(1)
- **O** 2 (2)
- **O** 3 (3)
- **O** 4 (4)
- **O** 5 (5)
- **O** 6(6)
- **O** 7(7)
- **O** 8 (8)
- **O** 9(9)
- **O** 10 (10)

Q9 Mood

- **O** 0 (0)
- **O** 1(1)
- **O** 2 (2)
- **O** 3 (3)
- **O** 4 (4)
- **O** 5 (5)
- **O** 6 (6)
- **O** 7 (7)
- **O** 8 (8)
- O 9(9)
- **O** 10 (10)

Q10 Walking Ability

- **O** 0 (0)

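### Secondary analyses: replace the significance-chosen covariates of section 12.4 with a fixed set, and give the baseline MBPI a stated role

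*Combined protocol and SAP*

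**What the plan says.** **Covariates.** Section 12.4 applies the same rule to the Cox model and to the repeated measures model: "The model will adjust for type of chemotherapy and other patient characteristics should they prove to be significant". The Protocol Synopsis, under statistical considerations, says that time to Grade E "will be assessed using the Cox proportional hazards model adjusting for type of chemotherapy", and that "QOL/Pain scores will be analyzed using a repeated measures model adjusting for type of chemotherapy". It mentions no further covariates. The primary analysis in 12.3 controls for chemotherapy type alone, with no selection.

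**Baseline MBPI.** Section 10.4.1 states that "The MBPI will be administered at the time of randomization" and at three later times: 40-50 Gy, end of radiation, and follow-up. Section 10.4 describes the outcome as "the quality of life and level of pain before, during, and after radiotherapy". Neither account of the repeated measures model has a baseline term or a constraint on the baseline means.

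**Scores.** Section 2.3.1 says: "There are seven pain severity items and seven pain interference items rated on a 0-10 Likert scale". Sections 1.2 and 10.4 speak of both quality of life and pain, and the MBPI is the only questionnaire. No section says which items make up which score, or which score and visit is the key comparison.

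**The concern.** Two analysts could fit different secondary models and each cite the protocol. One would follow the synopsis and use chemotherapy type only. The other would follow 12.4, and would first have to decide which characteristics to try, at what threshold and by what procedure. If those decisions are made after the arms are known, the reader of the results cannot tell how the model was reached.

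The baseline MBPI is a score the trial already pays to collect. Unless the model uses it in the right way, its precision is lost. The undefined scores add to the freedom. What is at stake is the credibility and precision of the secondary results, including the trial's only patient-reported evidence. The primary comparison is not at stake, and the baseline point does not concern the Cox model.

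**Working it through.** **1. Does the screen make the model depend on the sample?** The documents name no candidates, so the correlations and numbers of candidates here are assumptions. With n = 170, the chance that a characteristic with correlation r to the outcome passes p < 0.05 is about Φ(atanh(r)·√167 − 1.96). For r = 0.2: 0.2027 × 12.92 = 2.62, and Φ(0.66) = 75%. For r = 0.1 and 0.3 the chance is 25% and 98%. In simulation with 3 or 5 candidates at r = 0.1-0.2, the most common covariate set arose in only 24-47% of samples. So the final model is not known in advance.

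**2. Does the screen distort the test?** Simulated linear model for one visit, three strata, no treatment effect, 6000 runs per setting, 3, 5 or 8 candidates at r = 0.1 or 0.2:

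- automatic p < 0.05 screen: type I error 5.2-5.8%;
- chemotherapy type only: 4.7-5.3% (simulation error 0.3 points).

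A separate run of 4000 with covariate effects of 0.2 SD gave 5.2% (5 candidates) and 6.1% (10 candidates), against 4.9% unscreened. In that run, reporting the best of three models (chemotherapy only, screened, all candidates) gave 7.3% and 8.8%. The harm comes from freedom to choose, not from the screen itself. The Cox model was not simulated.

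**3. What is baseline MBPI worth?** Take SD 1, 85 per arm, and correlation ρ between baseline and a later visit (assumed). The variance of the arm difference at one visit is:

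- baseline ignored, or kept as a response with separate arm means: 2/85 = 0.0235;
- change from baseline: 4(1−ρ)/85;
- baseline adjusted for, or a response with arm means constrained equal: 2(1−ρ²)/85.

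| ρ | adjusted ÷ ignored = 1−ρ² | cut | equivalent N = 170/(1−ρ²) | change ÷ ignored = 2(1−ρ) |
|---|---|---|---|---|
| 0.1 | 0.99 | 1% | 172 | 1.80 |
| 0.2 | 0.96 | 4% | 177 | 1.60 |
| 0.3 | 0.91 | 9% | 187 | 1.40 |
| 0.5 | 0.75 | 25% | 227 | 1.00 |
| 0.7 | 0.51 | 49% | 333 | 0.60 |

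**4. Does the form of adjustment matter?** Yes, if the correlation fades over time. Assume baseline correlations of 0.7, 0.4 and 0.2 with the three later visits, and 0.5 between those visits. The constrained-response form has relative variance 1−ρ²: 0.51, 0.84, 0.96. A covariate with one slope b for all visits has 1 − 2bρ + b². The generalized least squares slope here is b = 0.58, which gives 0.52, 0.87 and, at the third visit, 1 − 2(0.58)(0.2) + 0.58² = 1 − 0.232 + 0.336 = 1.10. That is 10% worse than ignoring baseline. A baseline-by-visit interaction removes the problem.

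**5. Item count.** Stated: seven severity and seven interference items. In the questionnaire appendix:

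- Item Q1 rates skin discomfort 0-10 ("Q1 Please rate your current level of skin discomfort") and items Q2-Q5 rate pain 0-10, so there are five ratings, four of them worded as pain.
- Item Q6 is free text. Item Q7 is percent relief, on which 10 is the best answer.
- Items Q8-Q14 are the interference items: seven, as stated.

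Seven severity items are reached only by counting Q6 and Q7, which are not severity ratings.

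**The case against.** **The synopsis is only a short form of 12.4.** Both adjust for chemotherapy type, so there is no conflict over that factor. This stands. What remains is an unresolved choice about everything else.

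**Screening does no harm and may help.** A reader might infer from 12.4 that the secondary estimates are biased or the tests invalid. The documents and the simulations do not support that. A reader might also point to the movement of the estimate away from the chemotherapy-only value. At r = 0.2 that shift is 0.36 standard errors with screening and 0.37 with all candidates prespecified (3 candidates), and 0.47 and 0.48 (5 candidates). It is what any adjustment for prognostic covariates produces, so it is not evidence against selection. At r = 0.2 screening cuts variance by about 7% (3 candidates) and 15% (5). For that reason the remedy should allow named prognostic covariates and not forbid them.

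**Baseline does have a role.** Section 10.4 speaks of scores before, during and after radiotherapy, so the natural reading is that baseline is one of the repeated responses. This is fair. But with separate arm means at baseline, that reading gives no gain in precision (step 3). The gain needs equal baseline means or adjustment, and neither is stated.

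**The gain may be small.** Baseline is measured at randomization, before dermatitis is expected, so a correlation of 0.1-0.2 is plausible and the gain only 1-4%. This stands, and the range is reported for that reason.

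**Multiplicity.** A reader might count scores by visits and infer a large family of tests. No section plans such a family; the documents name only quality of life and pain.

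**Conclusion.** The point holds for the secondary analyses only. The rule in 12.4 leaves the covariate set of both models open, and the synopsis gives a different one. The consequence is a model that depends on the sample and on the analyst. It is not a biased estimate, nor a materially inflated error rate under an automatic screen.

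The precision of the baseline MBPI is not secured. Its value for a single visit ranges from 1-4% of variance (correlation 0.1-0.2) through 9% and 25% to 49% (0.3, 0.5, 0.7). These correlations are assumptions.

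The severity item count in 2.3.1 is wrong against the questionnaire, five and not seven, and the scores are undefined. Alone, these would be tidying; they belong in the same edit. The change is worth making because it costs almost nothing.

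**What to change.** 1. **Synopsis and 12.4, both models.** Delete the significance rule. State one fixed covariate set: chemotherapy type plus any prognostic baseline characteristics listed by name before unblinding.
2. **MBPI model.** Include visit and treatment-by-visit, with unstructured covariance. Enter baseline MBPI either as a response with arm means constrained equal at randomization, or as a covariate with a baseline-by-visit interaction. Do not use one common slope.
3. **Section 2.3.1.** Correct the severity count and define each score by item number, including which items form the quality-of-life score. Keep Q6 (free text) and Q7 (relief, opposite direction) out of any severity score.
4. **Key comparison.** The sponsor should name the key score and visit before unblinding. Item Q1, skin discomfort, deserves consideration, because the synopsis objective concerns pain associated with radiation dermatitis while Q2-Q5 ask about pain in general.

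**Cost.** Wording in three places, with no new data or patients. The models use a few more degrees of freedom, and the covariate form needs a rule for missing baseline scores, which the constrained form avoids.
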